10.2 Key Secondary Endpoints

The three key secondary endpoints and the corresponding primary analysis are as summarized and presented by pre-specified order in Table 1.

Biogen /	NightstaRx, Ltd
BIIB111	

The continuous efficacy endpoint will be analyzed by the analysis of covariance (ANCOVA) model including surgical group, baseline value of the assessment, and study arms. Missing data will be handled by the last observation carried forward (LOCF) approach.

The binary efficacy endpoints will be analyzed with the same method used for the primary efficacy endpoint with missing values imputed as failure.

The least square (LS) means, standard error (SE) and 95% CI will be reported for each treatment at each post-randomization visit. Least square mean, SE, 95% CI, and p-value for the between group differences will also be provided.

The primary analysis of the key secondary endpoints will be based on the ITT population, and supportive analyses will be performed based on the PP population and the randomized population. When performing the supportive analysis based on the randomized population, for subjects who do not have any post-baseline assessments, the baseline will be used when LOCF approach is applied (i.e. the change from baseline will be zero). Knowing the patients who had BCVA below 34 ETDRS letters at Month 12 for study eye, if any, will at site not be the responders of subjects with a ≥ 10 -letter improvement from Baseline in BCVA at Month 12, these subjects with minor protocol deviation will be included in the supportive analysis of the secondary endpoint of Proportion of subjects with a ≥ 10 -letter improvement from Baseline in BCVA at Month 12 measured by the ETDRS chart based on the PP population. When performing the supportive analysis based on PP population for the secondary endpoints of (a) Change from Baseline in BCVA at Month 12 measured by the ETDRS chart and (b) Proportion of subjects with no decrease from Baseline in BCVA or a decrease from Baseline in BCVA of <5 ETDRS letters at Month 12 measured by the ETDRS chart, subjects at site who had BCVA below 34 at Month 12 will be excluded from these analyses. The background information for site is described in Section 8.

Additional supportive analysis will be conducted by comparing the study eyes vs. the fellow eyes (i.e., contralateral control) within the low dose and the high dose treatment groups. The binary efficacy endpoints will be analyzed at the Month 12 visit using the paired McNemar test. Change from baseline in BCVA at Month 12 will be compared between the study eye and the fellow eye using the linear mixed model where the two eyes are considered correlated within each patient. The model will contain the variables for baseline BCVA, treatment groups (low dose and high dose), surgical group, eye (study eye vs fellow eye) and the treatment*eye interaction, where the eye variable acts as the repeat variable. (See sample SAS code in Appendix 5).

	Key Secondary Endpoint	Statistical Method
1	Change from Baseline in BCVA at Month 12 measured by the ETDRS chart	ANCOVA
2	Proportion of subjects with a ≥10-letter improvement from Baseline in BCVA at Month 12 measured by the ETDRS chart	Fisher's Exact Test; Fisher's Exact-Boschloo test with a Berger-Boos correction of beta=0.001; CMH Approach
3	Proportion of subjects with no decrease from Baseline in BCVA or a decrease from Baseline in BCVA of <5 ETDRS letters at Month 12 measured by the ETDRS chart	Fisher's Exact Test; Fisher's Exact-Boschloo test with a Berger-Boos correction of beta=0.001; CMH Approach

Tabla 1	Statistical Tests	for Vor	Secondamy	Efficient	Endnointe
Table 1	Statistical Lesis	IUI KEY	Secondary	Efficacy	Enapoints

Biogen / NightstaRy	x, Ltd
BIIB111	

Abbreviations: BCVA= best corrected visual acuity, CHM= choroideremia, ETDRS=Early Treatment of Diabetic Retinopathy Study

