9.6.1 AAV2-REP1 Treatment Groups vs Untreated Control Group, Assessor Masking

All ophthalmic assessments conducted during the Screening/Baseline period will be performed by appropriately qualified masked assessors. For the immediate post-operative visits, masking of the assessors will not be viable as clinical signs of surgery will be apparent (i.e. redness, swelling). Therefore, unmasked assessors will perform all ophthalmic assessments at Visit 3 (Day 1) and Visit 4 (Day 7). From Visit 5 (Month 1) onwards, masked assessors will be used, as any signs of surgery will have dissipated and it will not be possible clinically to differentiate between those subjects that have not undergone surgery, and those subjects that have undergone surgery and received active treatment.

Subjects randomised to the untreated Control group will not be required to attend the site at Visit 2, 3 or 4. As the key purpose of Visit 2 is surgery, and Visit 3 and 4, post-operative safety, there is limited utility in Control subjects attending. This will also limit the study burden for Control subjects, thereby potentially reducing the risk of subject withdrawal at this stage, and reducing the possibility of further unmasking due to direct contact and communication with fellow participants. Instead, a telephone contact from the site will occur for the Control group on Day 0 (Visit 2), Day 1 (Visit 3) and Day 7 (\pm 3 days; Visit 4).

In order to minimise bias further, masked assessors will not have access to the subject's medical records, source documentation or eCRF as data entries or notation (such as use of peri-operative corticosteroid) may be sources of unmasking. From Visit 5 (Month 1) onwards, the masked assessor will also read a pre-written statement to each subject, regardless of randomisation, reminding them of the masked nature of the study, and to avoid any reference to prior surgery/non-surgery, which eye may have received treatment or to allude to any information that may unmask the assessor as to which group the subject has been assigned to.

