13.2 Procedure for Accounting for Missing Data

All reasonable efforts will be made to obtain complete data for both eyes on all subjects. However, missing observations may occur. Management of dropout and missing observations will depend on their nature and frequency.

For binary efficacy endpoints (including the primary efficacy endpoint), missing data will be imputed as failure, to be conservative. For the continuous efficacy endpoints, the last observation carried forward (LOCF) approach will be utilized for handling missing data.

To evaluate the robustness of the results of the main analyses, sensitivity analyses of the primary and secondary endpoints will be performed. These analyses will include different imputation methods on different analysis sets and will be described in detail in the Statistical Analysis Plan.

Safety data will be analysed on observed data. Missing data will not be imputed.

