7.3 Intent-To-Treat Population

The Intent-to-Treat (ITT) population is defined as all subjects who are randomized, receive the study treatment (or the phone call for those in the untreated control group), and have at least one post-treatment BCVA measurement.

The ITT population will be used for the efficacy, quality of life, and

The primary population for efficacy analysis is the ITT population. Subjects will be analyzed based on the treatment to which they were randomized.

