10.4.2 Mixed Model Repeated Measures

For the change from baseline in BCVA, a mixed model repeated measures (MMRM) will be employed. The MMRM model will include treatment, visit (as a categorical variable), surgical group, baseline BCVA, treatment-by-visit interaction, and baseline BCVA-by-visit interaction.

An unstructured covariance matrix will be used for the within-subject correlation. The Kenward-Roger approximation will be used to estimate denominator degrees of freedom. In case of a convergence failure with the unstructured covariance, the following structures will be assessed in a sequential fashion until convergence is achieved: heterogeneous Toeplitz, Toeplitz, heterogeneous auto-regression, and auto-regression (See sample SAS code in Appendix 6).

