- ^b Study Visits 2, 3, and 4 only apply to subjects in the AAV2-REP1 groups. For subjects in the Control group, a telephone contact will be made at Visits 2, 3, and 4, and information regarding AEs/SAEs and concomitant medications, procedures, and treatments will be recorded.
- c End of Study Visit.
- ^d An ET visit should be performed if a subject discontinues at any time.
- e If clinically indicated, subjects may need to return to the site for an unscheduled visit. At a minimum, all assessments listed will be performed.
- ^f Informed consent must be signed within 12 weeks prior of dosing (Visit 2). The Screening/Baseline Visit must be performed within 8 weeks of dosing (Visit 2). Assessments and procedures conducted in the final visit of the NIGHT study (including the ET Visit) may be used for the Screening/Baseline Visit if the final NIGHT study occurs within 8 weeks prior to dosing (Visit 2).
- ^g Samples will be taken and retained for analyses, if necessary.
- ^h VFQ-25: to be completed only at sites where a validated translation is available. VFQ-25 must be completed by subjects at the beginning of the study visit, before any significant interaction with the study staff.
- ⁱ Weight is assessed for dose calculation for 21-day corticosteroid regimen.

Ι....

^k In order to capture accurate BCVA values at Visit 1 (Screening/Baseline), the following conditions apply to the BCVA assessment:

CONFIDENTIAL

DocuSign Envelope ID: 9EEC395C-0D7A-4605-B5D7-D5DF30B311BC

Biogen / NightstarRx, Ltd	Statistical Analysis Plan: 273CH301 / NSR-REP-01
BIIB111	11FEB2021

If the BCVA value at Visit 1 (Screening/Baseline) is $\geq \pm 10$ letter gain or loss in the study eye compared to the previous NIGHT study visit (if applicable), then BCVA must be repeated an additional 2 times, resulting in a total of 3 BCVA measures at Visit 1. To facilitate the additional BCVA measures this visit should be conducted over 2 days, with BCVA measured twice on Day 1 and once on Day 2. All 3 BCVA values must be recorded in the eCRF. The highest score will be used to define subject eligibility.

If the BCVA value at Visit 1 (Screening/Baseline) is $\leq \pm$ 10-letter difference in the study eye compared to the previous NIGHT study visit (if applicable), then BCVA will be collected once and will not be repeated.

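### LOCF for change in BCVA, the first key secondary endpoint, does not limit which visits may be carried, so an unmasked Day 1 or Day 7 reading can stand as a treated subject's Month 12 value

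*SAP*

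**What the plan says.** SAP 10.2 analyses change from baseline in BCVA at Month 12 by ANCOVA on the ITT population, and on gaps it says: "Missing data will be handled by the last observation carried forward (LOCF) approach". Protocol 13.2 has the same rule: "For the continuous efficacy endpoints, the last observation carried forward (LOCF) approach will be utilized for handling missing data". The one refinement, in SAP 10.2, applies to the supportive analysis of the randomized population: a subject with no post-baseline value gets his baseline, that is, a change of zero.

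The early visits differ by arm. Protocol 10.3 and 10.4 schedule BCVA at Day 1 and Day 7, but footnote b to the schedule in SAP Appendix 2 says: "Study Visits 2, 3, and 4 only apply to subjects in the AAV2-REP1 groups". Protocol 9.6.1 says of controls: "Subjects randomised to the untreated Control group will not be required to attend the site at Visit 2, 3 or 4". They are telephoned instead, and their first scheduled post-baseline BCVA is at Month 1. The same section says of masking at these visits: "unmasked assessors will perform all ophthalmic assessments at Visit 3 (Day 1) and Visit 4 (Day 7".

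ITT membership (SAP 7.3) requires, besides randomisation and treatment or the control telephone call, that subjects "have at least one post-treatment BCVA measurement". No timing is attached.

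For the same endpoint, SAP 10.4.2 says that "a mixed model repeated measures (MMRM) will be employed", and SAP 10.4.3 adds a control-based multiple imputation. Both are sensitivity analyses.

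**The concern.** LOCF takes whatever value is last. In the treated arms that can be a reading taken a day or a week after vitrectomy and retinal detachment. Protocol 12.3.1.2 itself foresees surgery-related losses of 15 letters or more within a day of surgery, and does not count them as serious adverse events if they recover. Such a reading says little about Month 12, and it was taken without the assessor masking on which this open-label design relies.

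The schedule gives controls no equivalent reading. Early loss to follow-up is therefore handled differently by arm, both in the value assigned and in whether the subject is counted at all.

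The endpoint is first in the fixed sequence after the primary (SAP 10.3). If it fails, the other two key secondary endpoints cannot be tested confirmatorily, and a favourable sensitivity analysis does not change that.

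**Working it through.** **1. The plan's own figures.** The documents give no effect size, SD or power for this endpoint. Their power statements concern the primary endpoint, and exact enumeration of Fisher's test reproduces them: 92.3% at 56 per arm (16.7% against 0%; stated as at least 90%) and 85.9% at 64 per arm with exactly one control responder (stated as 85%). They have no bearing on this point.

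**2. The route, side by side.** Take two subjects who are lost before Month 1 with no early termination or unscheduled BCVA.

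| | Treated | Control |
|---|---|---|
| Scheduled BCVA before Month 1 | Day 1 and Day 7, unmasked | none |
| In ITT (SAP 7.3) | yes | no |
| Month 12 value in the primary analysis | Day 1 or Day 7 reading | none |
| Randomized-population analysis (supportive) | Day 1 or Day 7 reading | change of zero |

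**3. What is not affected.** The primary endpoint and the main analyses of the two binary key secondary endpoints impute missing values as failure (SAP 10.1, 10.2). LOCF appears again for the binary endpoints as a sensitivity analysis (SAP 10.4.1) and for the other secondary endpoints (SAP 10.5). In the latter, SD-OCT also has Day 1 and Day 7 readings in treated subjects only, and autofluorescence has a Day 7 reading.

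**4. Size, on assumed inputs.** The arm size of 64 is from SAP 3.6. Assumed: true difference 5 letters (treated +5, control 0), SD 10, two-sided 0.05, and k high-dose subjects whose carried change is a loss of L letters. Let f = k/64 and g = 5 + L.

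- Expected estimate = 5 − f × g
- SE = √{[(1 − f) × 100 + f(1 − f) × g²]/64 + 100/64}
- Power ≈ Φ(estimate/SE − 1.96)

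Example, k = 1 and L = 20: estimate = 5 − 25/64 = 4.61, SE = 1.80, and 4.61/1.80 − 1.96 ≈ 0.60, so power is about 72%. Simulated two-sample t-tests (100,000 per cell) agree with the formula to within about 1 point:

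| Carried loss L | Estimate, k = 1 | Power, k = 1 | Estimate, k = 3 | Power, k = 3 |
|---|---|---|---|---|
| none carried | 5.00 | 80% | 5.00 | 80% |
| 5 letters | 4.84 | 78% | 4.53 | 72% |
| 10 letters | 4.77 | 76% | 4.30 | 67% |
| 15 letters | 4.69 | 74% | 4.06 | 60% |
| 20 letters | 4.61 | 72% | 3.83 | 53% |

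The SD matters as well. With k = 3 and L = 10 (normal approximation), power falls from 94% to 83% at SD 8, from 81% to 66% at SD 10, and from 65% to 51% at SD 12.

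**5. With a change of zero instead (L = 0).** The estimate is 5 − 5/64 = 4.92 for k = 1 and 5 − 15/64 = 4.77 for k = 3, with power of about 79% and 77%.

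**The case against.** **The route is narrow.** It needs a treated subject with no BCVA at Month 1 or later. Sites must make every reasonable effort to hold an early termination visit (Protocol 8.3, 10.9), and BCVA is required there and at unscheduled visits (10.10). The documents give no early dropout rate. This stands: the number may be small, or none.

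**Large losses belong mainly to Day 1.** The reporting exemption in Protocol 12.3.1.2 expects the loss to be recovering by Day 7, so a 20-letter carried loss mostly requires that Day 7 was missed too. This stands, and is why the table starts at 5 letters.

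**The error hurts the sponsor.** A reader might infer that the rule could manufacture a benefit or undermine the trial's main result. The documents do not support that. Carried post-operative readings would more likely lower the treated mean, though this is not guaranteed. The sequence reaches this endpoint only after the primary has succeeded, and the primary does not use LOCF.

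**Day 1 and Day 7 may not be analysis visits.** SAP 5.1 lists Baseline, Months 1, 4, 8, 12 and End of Study. That list governs descriptive summaries and is not a carry-forward rule, so it does not close the gap.

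**Other analyses cover it.** The MMRM, the control-based imputation and the randomized-population analysis would help interpretation. None replaces the confirmatory test.

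**Conclusion.** The point holds as a gap in the primary analysis of one endpoint. As written, the SAP allows an unmasked, immediate post-operative BCVA to count as a Month 12 outcome, and the schedule creates such readings only in the treated arms. A control could have an early unscheduled or termination BCVA, but that is a different and unscheduled route.

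The probable consequence is attenuation and lost power on the test that gates the second and third key secondary endpoints. On the assumed values, the loss is about 2 to 8 percentage points of power for one affected subject and about 8 to 27 for three. The difference, SD, carried loss and number affected are all assumptions, so this is a sensitivity range and does not predict what will happen.

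It would be wrong to infer that a control lost early never counts. He is outside ITT, but enters the randomized-population analysis with a change of zero. The change should be made because it is cheap and removes an arm-specific artefact, even though that artefact may prove small.

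**What to change.** **Minimum change.** Wherever LOCF is used (SAP 10.2, 10.4.1, 10.5), state that Day 1 and Day 7 values are not carried. Carry only assessments from Visit 5 (Month 1) onward, including early termination and unscheduled assessments from that time. Flag those made by an unmasked assessor, because Protocol Table 1 assures masking only at Visits 1 and 5 to 8. For an ITT subject with no such BCVA, state the value used, for example baseline carried forward (change of zero), as the SAP already does for the randomized population. He then stays in the analysis.

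**Preferred change.** Make the MMRM of SAP 10.4.2 the primary analysis of change in BCVA, and state its visits as Months 1, 4, 8 and 12, which that section does not list. Keep the unrestricted LOCF and the control-based imputation of SAP 10.4.3 as sensitivity analyses.

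**Cost.** Either change needs SAP wording. The MMRM is specified, but the documents do not show that it has been programmed. A lasting surgical loss in a subject who leaves before Month 1 would no longer be carried in the main analysis, and in the MMRM that subject contributes no outcome, which could favour the product. The retained sensitivity analyses keep such cases visible. The ITT definition would still admit early treated leavers and not early control leavers, so the randomized-population analysis should be reported alongside.

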10.3 Multiplicity Adjustment

The protection of the type I error will be achieved for the comparison between the high dose and the untreated control under a hierarchical procedure. The primary efficacy endpoint will be first tested. If the p-value is <0.05, the study will be declared positive and the key secondary endpoints will be tested in the pre-specified order mentioned in Table 1. The comparison between the low-dose arm and the untreated control is considered as supportive and will be performed only if significance is achieved between the high dose and the untreated control on the same efficacy endpoint.

No multiplicity adjustment will be performed for the Data Monitoring Committee's (DMC) analysis of safety monitoring.

10.4 Sensitivity Analyses for Handling Missing Data

Sensitivity analyses will be performed based on the ITT population to evaluate the robustness of the primary and the key secondary endpoints and to assess the impact of missing data.

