10.4.3 Multiple Imputation Based on Missing Not at Random

For the change from baseline in BCVA, the pattern-mixture model using a control-based multiple imputation method will be performed based on missing data not at random for the ITT population. The method described here is based on methodology described by Little and Yau (1996) and extended in Ratitch and O'Kelly (2011). It assumes that subjects who discontinue from the study would have the same evolution of the disease as those subjects on the control group who remained in the study. The assumption that efficacy profiles of dropouts after discontinuation are similar to those of untreated control subjects is considered conservative because this methodology tends to minimize the difference between treatment and control groups. If the results of this analysis are in line with the primary efficacy results, then it can be confidently concluded that the primary analysis results are robust.

Biogen / NightstaRx,	Ltd
BIIB111	

Using this method, missing data after discontinuation will be imputed based on control group data using multiple imputation methodology for all subjects (including treatment subjects).

The steps to implement this sensitivity analysis are as follows (See sample SAS code in Appendix 7):

- 1. 100 datasets will be generated where missing data at intermediate visit(s) will be imputed for each treatment group using non-missing data from all subjects within the treatment group by a Monte Carlo Markov Chain (MCMC) imputation model using the MCMC statement in the SAS PROC MI procedure. As a result, each dataset will only have missing ending data, or a monotone missing data pattern.
- 2. For each dataset from Step 1, missing ending data will be imputed based on information from the control group. As a result, 100 imputed complete datasets will be generated.
 - Missing data at the first post-baseline visit will be imputed by a regression imputation model using the SAS PROC MI procedure with the REGRESSION option in the MONOTONE statement.
 - The SAS PROC MI procedure will use data from all control subjects as well as treatment subjects with missing data at the visit (i.e., only those that need imputation at the visit). Because subjects from treatment groups without missing data at the visit are excluded from this step, they will not contribute to the estimation of the imputation model for the visit.

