10.5 Other Secondary Efficacy Endpoints

For the analysis of the following efficacy endpoints, the same analysis of covariance (ANCOVA) model will be utilized based on the ITT population with missing data handled by the LOCF approach.

- Change from Baseline in BCVA at Months 4, 8 and 12
- Change from Baseline at Month 12 in:
 - Total Area of Preserved AF
 - Distance from Foveal Center (FC) to nearest Border of Preserved AF
- Change from Baseline in the following SD-OCT variables at Month 12:
 - Foveal Subfield Thickness
 - Total Macular Volume
 - Central Horizontal Ellipsoid Width

- Central Ellipsoid Area
- Choroidal Thickness
- Change from Baseline in the following microperimetry variables at Month 12:
 - Mean Sensitivity
 - Bivariate Contour Ellipse Area 63%
 - Bivariate Contour Ellipse Area 95%
- Change from Baseline in contrast sensitivity score at Month 12
- Change from Baseline in colour vision at Month 12
- Change from Baseline in reading speed test at Month 12
 - The reading speed will be calculated using the following formula: [number of words in the text number of misread words] / reading time x 60. The number of words per text is available in Appendix 1: IRest Reading Speed Test, Conversion Table, while the number of misread words and reading time will be collected in the case report form (CRF).
- Change from Baseline in the 25-item VFQ-25 overall score and sub-scale scores at Month 12
 - The VFQ-25 patient questionnaire consists of 25 vision-related questions, each of them pertaining to one of the 11 vision-related subscales. For each subscale, a score is calculated. Scores are between 0 and 100, where a higher value represents better functioning. The overall composite score is calculated as the mean of the sub-scale scores (Mangione 2000).

CONFIDENTIAL

CONFIDENTIAL

Page 27 of 46

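### Protocol 13.2 promises missing-data sensitivity analyses of the secondary endpoints, but SAP 10.4 stops at the key secondary ones and leaves preserved AF and ellipsoid area on LOCF alone

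*SAP*

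**What the plan says.** Protocol 13.2 sets the main rule: "For the continuous efficacy endpoints, the last observation carried forward (LOCF) approach will be utilized for handling missing data". It then states that "sensitivity analyses of the primary and secondary endpoints will be performed", and adds: "These analyses will include different imputation methods on different analysis sets and will be described in detail in the Statistical Analysis Plan". The protocol lists key secondary endpoints (6.2.2) and other secondary endpoints (6.2.3) under separate headings, so the unqualified word in 13.2 naturally covers both.

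SAP 10.4 runs its missing-data analyses on the ITT population, with the purpose "to evaluate the robustness of the primary and the key secondary endpoints and to assess the impact of missing data". Three methods follow:

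- LOCF for the binary endpoints (10.4.1).
- A repeated-measures model: "For the change from baseline in BCVA, a mixed model repeated measures (MMRM) will be employed" (10.4.2).
- Control-based imputation: "For the change from baseline in BCVA, the pattern-mixture model using a control-based multiple imputation method will be performed" (10.4.3).

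SAP 10.5 covers the other secondary endpoints, including total preserved AF area, central horizontal ellipsoid width and central ellipsoid area. They are analysed by ANCOVA "based on the ITT population with missing data handled by the LOCF approach". No second method is named.

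**The concern.** Two things meet here. The first is a textual gap: the protocol promises more than the SAP delivers, and the SAP does not say so. Elsewhere the SAP does announce a departure. Section 7.4 labels its change to the per-protocol definition as a correction of the protocol.

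The second is where the gap falls. Both documents describe choroideremia as degenerative, and Protocol 11.8 uses AF to track the area of viable retina. These areas are expected to shrink. Under LOCF, an eye last imaged at Month 4 is credited with no further loss for the remaining 8 months. If the arms differ in how many subjects are missing, or in when they leave, the estimated difference in preserved area moves for reasons unrelated to treatment. At stake is the reliability of the structural estimates, not the trial's primary test.

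**Working it through.** **Text comparison**

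| | Primary and key secondary | Preserved AF and ellipsoid variables |
|---|---|---|
| Protocol 13.2 | sensitivity analyses promised | sensitivity analyses promised |
| SAP 10.4.1 to 10.4.3 | LOCF (binary); MMRM and control-based MI (BCVA change) | none |
| SAP 5.5 (COVID-19) | further sensitivity analyses, including MAR multiple imputation | none |
| SAP 7.1, 7.4, 10.1, 10.2 | supportive per-protocol and randomised-population analyses | none |
| SAP 10.5 | not applicable | ANCOVA, ITT, LOCF |

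One other secondary endpoint, BCVA change at Months 4 and 8, is reached incidentally by the BCVA MMRM. The imaging endpoints are not.

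**Size of a possible LOCF shift**

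The plan has no figure of its own to reproduce. The sample-size calculation concerns the primary endpoint only, and no decline rate, standard deviation or dropout rate is given for AF or ellipsoid area. The one progression figure, an average loss of 0.5 letters over 20 months (SAP 5.5), is for acuity and cannot be turned into an area. What follows is therefore illustrative.

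Assumptions:

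- L is the control arm's 12-month area loss, and loss is linear.
- Treatment slows loss by a share s, taken as 20-30%, so the treated arm loses (1 - s)L.
- dT and dC are the shares missing at Month 12 in the treated and control arms. f is the fraction of the year not observed.
- Subjects who leave would have lost area at their arm's rate.

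LOCF understates mean loss by dT x f x (1 - s)L in the treated arm and by dC x f x L in control. The shift in the treated-minus-control difference is

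(dT x f x (1 - s) - dC x f) x L, where positive favours treatment.

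*10% v 3% missing after Month 4* (f = 8/12):

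- s = 20%: 0.10 x 0.667 x 0.8 - 0.03 x 0.667 = 0.0533 - 0.0200 = 3.3% of L.
- s = 30%: 0.0467 - 0.0200 = 2.7% of L.

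*20% v 5% missing after Month 1* (f = 11/12):

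- s = 20%: 0.20 x 0.917 x 0.8 - 0.05 x 0.917 = 0.1467 - 0.0458 = 10.1% of L.
- s = 30%: 0.1283 - 0.0458 = 8.3% of L.

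As a share of the assumed effect, these run from 2.7/30 = 9% to 10.1/20 = 50%.

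*Imbalance reversed* (3% v 10% after Month 4, s = 20%): 0.03 x 0.667 x 0.8 - 0.10 x 0.667 = 0.016 - 0.067 = -5.1% of L, against treatment.

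*Equal dropout* (10% in each arm after Month 4): the shift is -d x f x s x L. With s = 20% this is -0.10 x 0.667 x 0.20 = -1.3% of L. The true effect shrinks by d x f = 6.7% of itself.

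**Feasibility of the alternative**

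Protocol Table 3 schedules AF and SD-OCT in all arms at Months 1, 4, 8 and 12, so the SAP 10.4.2 model can be fitted to these measures as it stands.

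**The case against.** The best case for the plan has several parts.

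- **The protocol chose LOCF.** SAP 10.5 follows the protocol's main method, and 13.2 leaves the detail of the sensitivity analyses to the SAP. This stands. The inconsistency is the missing sensitivity analysis, not LOCF as the main analysis. Leaving detail to the SAP does not, however, remove endpoints from the commitment.
- **For the endpoints that matter most, the promise is kept.** The SAP does provide "different imputation methods on different analysis sets" for the primary and key secondary endpoints through its per-protocol, randomised-population and COVID-19 analyses. This also stands.
- **Dropout would not be hidden.** A reader might infer that nothing planned could expose differential dropout. That is wrong. SAP 13 examines the number, pattern and timing of missing data by arm, with Kaplan-Meier time to discontinuation. SAP 6 gives disposition by arm, and SAP 5.1 summarises efficacy by visit with End of Study as a separate entry. These would reveal an imbalance. They would not show how far it moves the Month 12 AF or ellipsoid estimate.
- **Early termination imaging.** Protocol 10.9 includes AF and SD-OCT at the early termination visit, so a carried value may be later than the last scheduled one. This reduces the shifts above.
- **Low stakes.** These endpoints lie outside the type I error hierarchy in SAP 10.3. This stands and limits the severity.
- **SAP 10.6 cannot be read.** Its text is not visible, so nothing is held against the plan on that account. Sections 10.4 and 10.5 are explicit on their own.

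**Conclusion.** The gap between Protocol 13.2 and SAP 10.4 is real and undeclared, and it leaves preserved AF area and the ellipsoid variables with a single missing-data method. Under the stated assumptions, the LOCF shift is 2.7-3.3% of annual control loss in the moderate scenario and 8.3-10.1% in the heavy, early one. The dropout shares, the slowing and linear loss are all assumed, so the actual size is unknown. The primary and key secondary conclusions do not depend on it.

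Three stronger readings are not supported:

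- That LOCF will flatter treatment. The sign depends on which arm loses more subjects and when. Reversed imbalance counts against treatment, and equal dropout dilutes a true effect.
- That the shift is 4.7% or 13.8% of L. Those values come from applying one loss rate to both arms: (0.10 - 0.03) x 8/12 and (0.20 - 0.05) x 11/12. That assumes no treatment effect, so they cannot be set against an assumed slowing.
- That the LOCF standard errors are shown to be too small. That is a general caution about single imputation, and nothing here calculates it.

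This should be corrected, but it does not threaten the trial's main result.

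**What to change.** Extend SAP 10.4 so that the 10.4.2 MMRM is also run on total preserved AF area and the ellipsoid width and area in 10.5. Use Months 1, 4, 8 and 12, with terms for treatment, visit, surgical group, the baseline value of the measure, treatment-by-visit and baseline-by-visit. Report it beside the LOCF ANCOVA as a sensitivity analysis.

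No rule is needed that a statement about preserved area must rest on the two results agreeing. Protocol 13.2 does not ask for one, and it would be a new decision rule for endpoints outside the hierarchy.

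For other secondary endpoints still left without a sensitivity analysis, one sentence should declare and justify the narrower scope as a change from Protocol 13.2. Reading speed and VFQ-25 are scheduled only at baseline and Month 12 or early termination, so a repeated-measures model adds little there.

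The cost is SAP wording before database lock and a few more runs of a model already specified. No new data are required.
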